## **8.0 Reporting of Adverse Events or Unanticipated Problems involving Risk to Participants or Others**

Safety information will be assessed by subject interview. As these results are collected, all adverse events (AE) will be identified and reported to the principle investigator within fourteen (14) days. Adverse events will be reported as described below. The principal investigator (PI) is responsible for evaluating each AE and for determining whether the AE affects the risk/benefit ratio of the study and whether modifications to the protocol and consent form are required.

Treatment will be discontinued for any subject who develops conditions during the course of the study that are felt to significantly alter the risk/benefit profile for the individual subject.

**Adverse event grading.** All adverse events will be graded as follows:

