**Figure 1: Study Protocol**

**Safety Precautions:** In this protocol we have the following safety precautions: (1) Anti-hypertensive/diuretic medications (like the ones used in this study) may lower blood pressure excessively and/or alter serum electrolyte levels. Accordingly, we will monitor blood pressure and electrolyte levels throughout the study. Subjects who develop electrolyte imbalance will receive an electrolyte supplement or be asked to slightly change their diet. (2) Since the use of diuretics during pregnancy introduces unnecessary risk, female subjects will have a urine pregnancy test at each study visit before any research procedures are performed. (3) Since the presence of any metal introduces unnecessary risk, a screening X-ray exam will be performed to confirm the absence of any metal in subjects where that is a possibility.

**Permanent stopping criteria:** A patient will be terminated from the study for any of the following reasons:

- Persistent hyperkalemia ( $K > 5.5$  mmol/L) occurs;
- Any allergies to the drugs develop;
- Women who become pregnant;
- There are any adverse events or clinical events that the PI judges increases the risk to the patient;
- There are any signs or symptoms of decline or deterioration of their health status.

**Screening Visit:** Within about two weeks up to the start of the Treatment Phase (which begins after the Baseline Visits) and after the subject has provided informed consent, the following information will be collected:

- Demographics
- Medical history
- Concomitant medications

Also, the following procedures and assessments will be performed:

- Vital signs (including blood pressure)
- Physical exam

- CMP (comprehensive metabolic panel) unless there is a documented CMP within 1 month of the stipulated study entry date as part of routine medical care
- Pregnancy test
- X-ray exam

**Baseline Visits (Week 0):** Subjects that qualify for the study will be randomized to one of the study arms, and will be asked to come in a fasted state on two separate days (preferably consecutive but no more than about 4 weeks apart) to the General Clinical Research Center (GCRC). On one of the visits, a hyperinsulinemic euglycemic clamp (HEGC) study will be performed. At the other visit, NaMRI and pulse wave velocity (PWV) will be performed, as well as a hand grip test. These procedures are described below.

At the Baseline Visits, the following information will be collected:

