### Severity

- 0 = No adverse event or within normal limits
- 1 = Mild—did not require treatment
- 2 = Moderate—resolved with treatment
- 3 = Severe—required professional medical attention
- 4 = Life-threatening or disabling
- 5 = Death

Related to study drug (there is a reasonable possibility that the experience may have been caused by the drug)

- 0 = Unrelated
- 1 = Unknown
- 2 = Related

Unexpected event (an AE with specificity or severity not consistent with the risk information in the protocol/application or an AE that has not been previously observed)

- 0 = No
- 1 = Yes

Serious (any AE occurring at any dose that results in death; a life-threatening adverse drug experience; inpatient hospitalization or prolongation of existing hospitalization; a persistent or significant disability/incapacity; a congenital anomaly/birth defect; or any important medical event that, based on medical judgment, jeopardizes the subject and may require medical or surgical intervention to prevent one of the above outcomes)

- 0 = No
- 1 = Yes

**Adverse event reporting.** Any adverse experience associated with the use of drug that is serious, unexpected and possibly or definitely study related will be reported in writing to the IRB within 10 working days of the PI's first knowledge of the occurrence. The PI will review all expedited adverse event reports. In addition, any deviations from protocol will be reported to the IRB.

The annual summary of all adverse events and any audit reports will be sent to the IRB and to the study DSMB.

**Data Safety and Monitoring Board (DSMB).** We will establish a DSMB for the purposes of this study. The board will consist of the following member from the Vanderbilt University Medical Center:

[name] (Associate Director, CRC); Chair

The DSMB will regularly monitor study progress. On an annual basis, the DSMB will also review adverse event logs and any preliminary data. DSMB summary reports will be provided to the IRB according to the IRB's policies and procedures. No interim analysis is planned. Annual progress reports will be submitted to VICTR.

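### Section 8.0 gives serious adverse events the same 14-day limit to reach the PI as any other event, and the IRB reporting clock starts only once the PI knows

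*Combined protocol and SAP*

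**What the plan says.** Section 8.0 has safety information collected by interviewing subjects and sets a single limit: "all adverse events (AE) will be identified and reported to the principle investigator within fourteen (14) days". It makes the PI responsible for evaluating each event, including "determining whether the AE affects the risk/benefit ratio of the study" and whether the protocol or consent form must change.

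Further down, Section 8.0 grades severity from 0 to 5 and defines seriousness by the usual outcomes, among them "inpatient hospitalization or prolongation of existing hospitalization". Under its adverse event reporting heading, an event that is associated with use of the drug, serious, unexpected and at least possibly study related is to be "reported in writing to the IRB within 10 working days of the" PI's "first knowledge of the occurrence". The PI is to review expedited reports, with no time attached. The DSMB looks at adverse event logs once a year.

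Two other provisions bear on the point. The permanent stopping criteria in Section 6.0 include "There are any adverse events or clinical events that the PI judges increases the risk to the patient" and, separately, "There are any signs or symptoms of decline or deterioration of their health status". Section 8.0 also has a general rule that begins "Treatment will be discontinued for any subject who develops conditions during the course of the study" and covers conditions felt to alter that subject's risk/benefit profile.

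**The concern.** The protocol uses its definition of serious to select events for the IRB. It does not use it to speed notice to the PI. The 14-day limit covers all events, so a death or life-threatening event may take as long to reach the PI as a mild headache.

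Patient safety is at stake. Until the PI knows, nobody named in the plan is charged with asking whether the event changes the risk for the other enrolled subjects. The stopping criterion that needs PI judgement cannot operate, and for events that qualify for IRB reporting the clock has not started. Treatment lasts 8 weeks (56 days), so 14 days is 14/56 = a quarter of a subject's time on treatment.

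**Working it through.** **Inputs, all from the combined protocol and SAP**

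- Staff to PI: 14 days, all adverse events (Section 8.0). The text does not say whether these are calendar or working days, and does not define the start precisely.
- PI to IRB: 10 working days from the PI's first knowledge (Section 8.0, adverse event reporting).
- Treatment: 8 weeks, with adverse events collected at Weeks 2, 4 and 8, and drug dispensed at Weeks 0 and 4 (Section 6.0).

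**Assumptions:** the 14 days are calendar days, they run from the working day on which staff learn of the event, and there are no public holidays.

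**Step 1. Is there a faster route to the PI?** Each candidate was set against the 14-day rule.

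| Provision | What it does | Sets a time for the PI to be told? |
|---|---|---|
| PI review of expedited reports (8.0) | Review duty only | No |
| DSMB (8.0) | Annual log review; regular monitoring of progress without a schedule | No |
| Unblinded treating physician (5.0) | Guides decisions on abnormal potassium | No |
| Potassium, allergy and pregnancy stopping criteria (6.0) | Withdraw the individual subject | No |
| General discontinuation rule (8.0) and health-decline criterion (6.0) | Stop the individual subject; name no PI and no clock | No |
| Clamp monitoring (6.0, 7.0) | Manages the subject during the procedure | No |

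No route shortens the 14 days.

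**Step 2. Present ceiling**

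- Staff to PI: 14 calendar days, which falls on the same weekday as the start.
- PI to IRB: 10 working days = 2 weeks = 14 calendar days.
- Staff awareness to IRB: 14 + 14 = **28 calendar days**, which is 28/56 = half of the treatment period.

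If the 14 days are working days, the total is 14 + 10 = 24 working days. That is 4 full weeks (28 calendar days) plus 4 working days (4 to 6 calendar days), so 32 to 34 calendar days.

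**Step 3. Ceiling with next-working-day notice**

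- Learned Monday to Thursday: PI told at +1 day; IRB by 1 + 14 = 15 days.
- Learned Friday: PI told Monday at +3 days; IRB by 3 + 14 = 17 days.
- Gain at the IRB: 28 − 17 = 11 to 28 − 15 = 13 days.
- Gain at the PI: 14 − 3 = 11 to 14 − 1 = 13 days.

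**Step 4. Against the visit schedule.** An event learned at the Week 2 visit need not reach the PI until about Week 4 (2 + 2 weeks), when drug is dispensed again. An event learned between those visits need not reach the PI until after that dispensing. This shows what the rule permits. It does not show that a subject would be given more drug, because the subject-level rules in Step 1 may act first.

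The limit appears to run from collection of the information, not from onset. Where an event comes to light only at a visit interview, the time from onset can be longer still: the longest gap between visits that collect adverse events is 4 weeks (Week 4 to Week 8).

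**The case against.** The strongest reply is that the 14 days are an outer limit. Section 8.0 has events identified and reported as results come in, the trial runs at one medical center, and nothing tells staff to wait. This stands: the figures are ceilings, and no actual delay is shown.

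Second, the main foreseeable hazards have their own safeguards: blood pressure and electrolyte checks at each visit, an unblinded physician for potassium, stopping criteria for persistent hyperkalemia, allergy and pregnancy, immediate discontinuation on self-reported pregnancy, and close monitoring during the clamp. This narrows the worry for the affected subject. It does not touch the study-level evaluation or the IRB clock, since none of these provisions says when the PI must be told.

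Third, the 10-working-day clock covers only a subset of serious events. This is correct, and the 28-day figure applies to that subset alone. Other serious events reach the IRB through the annual summary, but the 14-day limit to the PI still governs them.

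Fourth, the proposed wording has limits. A condition tied to dispensing can act only at Week 4, never in the diet arm, and does not recall drug already at home. One limb of the definition of serious rests on medical judgement, so someone must apply it before the PI is told. Both remarks are fair. The next-working-day notice works without the dispensing condition, and most limbs of the definition are factual outcomes that staff can recognize. The choice of one working day is a recommendation; the protocol does not supply that figure.

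**Conclusion.** The concern holds. Read as written, Section 8.0 allows 14 days before the PI must know of a serious event in any of the four arms. It allows 28 calendar days before the IRB must receive a report of an event that is serious, unexpected, at least possibly study related and associated with drug use. The 28-day figure rests on the calendar-day, start-of-clock and no-holiday assumptions above; if the 14 days are working days, it is 32 to 34.

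The consequence established is possible delay to three things: the PI's study-level evaluation, the PI-judged stopping criterion, and the IRB report. Delay in stopping drug for the affected subject is possible but not shown. The documents give no expected number of serious events, so the number of subjects affected cannot be stated. The change is worth making because it serves patient safety and costs little, but the trial's design and analysis do not depend on it.

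**What to change.** Add one sentence to Section 8.0:

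> Any event that meets the definition of serious, or is graded severity 4 or 5, will be reported to the PI by the next working day after study staff learn of it, and before any further study drug is dispensed to that subject.

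Keep 14 days for all other events. That includes grade 3 events that are not serious, since grade 3 in this protocol means only that professional medical care was needed.

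The cost is slightly more prompt reporting work for staff and, for an event known before the Week 4 visit, holding that dispensing until the PI has been told. Design, visits and analysis do not change.

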### Severity

- 0 = No adverse event or within normal limits
- 1 = Mild—did not require treatment
- 2 = Moderate—resolved with treatment
- 3 = Severe—required professional medical attention
- 4 = Life-threatening or disabling
- 5 = Death

Related to study drug (there is a reasonable possibility that the experience may have been caused by the drug)

- 0 = Unrelated
- 1 = Unknown
- 2 = Related

Unexpected event (an AE with specificity or severity not consistent with the risk information in the protocol/application or an AE that has not been previously observed)

- 0 = No
- 1 = Yes

Serious (any AE occurring at any dose that results in death; a life-threatening adverse drug experience; inpatient hospitalization or prolongation of existing hospitalization; a persistent or significant disability/incapacity; a congenital anomaly/birth defect; or any important medical event that, based on medical judgment, jeopardizes the subject and may require medical or surgical intervention to prevent one of the above outcomes)

- 0 = No
- 1 = Yes

**Adverse event reporting.** Any adverse experience associated with the use of drug that is serious, unexpected and possibly or definitely study related will be reported in writing to the IRB within 10 working days of the PI's first knowledge of the occurrence. The PI will review all expedited adverse event reports. In addition, any deviations from protocol will be reported to the IRB.

The annual summary of all adverse events and any audit reports will be sent to the IRB and to the study DSMB.

**Data Safety and Monitoring Board (DSMB).** We will establish a DSMB for the purposes of this study. The board will consist of the following member from the Vanderbilt University Medical Center:

[name] (Associate Director, CRC); Chair

The DSMB will regularly monitor study progress. On an annual basis, the DSMB will also review adverse event logs and any preliminary data. DSMB summary reports will be provided to the IRB according to the IRB's policies and procedures. No interim analysis is planned. Annual progress reports will be submitted to VICTR.

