## 5.0 Enrollment/Randomization

The study will be conducted at the Vanderbilt University Medical Center. Institutional Review Board approval and written informed consent will be obtained from all study subjects.

We propose to study a total of 200 subjects controlled for race (50% African Americans, 50% Caucasians) and gender (50% female, 50% male). Subjects will be recruited from the Outpatient Clinics at VUMC (including the General Medicine Clinic and the Hypertension Clinic), as well as by emails, flyers, and other recruitment tools. All participants will have a baseline assessment, as well as on-going monitoring, of their health status as documented in their medical record.

[figure not shown]
Subjects will be randomly assigned to one of the study arms (diet, spironolactone, chlorthalidone, or placebo). Randomization will be determined using a stratified permuted-block randomization method. Stratification will be based on gender and race.

One treating physician will be unblinded as to whether subjects are receiving spironolactone or chlorthalidone and will guide decisions regarding subjects who develop abnormal serum potassium levels.

To specifically address Aims 1, 3 and 4, we will also enroll subjects who will only complete visits through Week 0. In addition, to aid data analysis, we will also re-enroll subjects who will complete a follow-up visit consisting of a blood draw.

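### Adverse-event severity grades 1 to 3 are defined by treatment and medical attention, overlap, and leave a gap, so they do not reliably measure severity

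*Combined protocol and SAP*

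**What the plan says.** Section 8.0 of the combined protocol and SAP introduces the scale with "All adverse events will be graded as follows", so it covers symptoms and laboratory findings alike. No separate laboratory scale is given. The first three non-zero grades are:

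- "1 = Mild—did not require treatment"
- "2 = Moderate—resolved with treatment"
- "3 = Severe—required professional medical attention"

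The next level, "4 = Life-threatening or disabling", and grade 5 (death) are defined by consequence. Relatedness, unexpectedness and seriousness are scored separately.

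Two other sections govern the potassium events that the trial monitors. Under the safety precautions in Section 6.0, "Subjects who develop electrolyte imbalance will receive an electrolyte supplement or be asked to slightly change their diet". The stopping criteria there end participation for persistent potassium above 5.5 mmol/L. Section 5.0 has one treating physician, unblinded as to spironolactone or chlorthalidone, who "will guide decisions regarding subjects who develop abnormal serum potassium levels".

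The annual summary of adverse events goes to the IRB and the DSMB, and the DSMB reviews the event logs once a year.

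**The concern.** A severity grade should say how bad an event was. Grades 1 to 3 here say whether treatment was needed, whether it worked, or whether a professional was required. These are three different attributes, not three levels of one attribute, so nothing makes the grades exclusive or complete.

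The people who watch safety in this trial see the event logs and the annual summary. If the grade depends on handling, a shift in grades could reflect a shift in handling. For potassium, the handling is guided by someone who knows which drug the subject takes, so the grade can carry that knowledge into an otherwise double-blind drug comparison. For symptoms such as gastrointestinal upset, headache or dizziness (Section 7.0), safety information is gathered by interview (Section 8.0). No scheduled measurement exists from which the severity of such a symptom could be recovered later.

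**Working it through.** No arithmetic applies. The check is to classify each grade and then apply the printed words to events that the protocol foresees.

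**Step 1: what each grade measures.** Grade 1: need for treatment. Grade 2: response to treatment. Grade 3: need for professional attention. Grade 4: threat to life, or disability. Grade 5: death. Three of the five non-zero grades concern management and two concern consequence.

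**Step 2: are grades 1 to 3 exclusive and exhaustive?**

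- Overlap: an event that needs a clinician, is treated and resolves satisfies grades 2 and 3. No tie-break rule is given.
- Gap: an event that needs treatment, is treated, does not resolve, receives no professional attention and is neither life-threatening nor disabling satisfies none of grades 1 to 5. It is not grade 0 either, because an event occurred.

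**Step 3: symptoms.** A trivial headache that resolves after a remedy is grade 2. An intense headache that passes without treatment can be grade 1. The order of the grades is then the reverse of the order of intensity.

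**Step 4: potassium events.** Two points of reading are left open: whether the physician's guidance counts as professional medical attention, and whether a diet change counts as treatment. The grades each event can receive are:

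| Event | Admissible grades | Why |
|---|---|---|
| Low potassium, supplement given, resolves | 2 or 3 | 2 as resolved with treatment; 3 if the physician's guidance counts |
| Persistent potassium above 5.5 mmol/L, participation ended, no treatment given (assumed here; Section 6.0 does not say) | 1 or 3 | 1 if ending participation is not treatment; 3 if the physician's guidance counts |
| High potassium handled by a diet change | 1, 2 or 3 | 1 if diet is not treatment; 2 if it is and the event resolves; 3 if the physician's guidance counts |

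One reading places an event that ends participation at grade 1, below a corrected low potassium at grade 2. Another reading places all three at grade 3. Nothing in the text chooses between them.

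**Step 5: what uses the grade.**

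- Section 10.0 plans no analysis of severity by arm.
- The report due within 10 working days requires an event to be serious, unexpected and possibly or definitely study related. Seriousness has its own outcome-based definition.
- Severity enters the definition of unexpected, "an AE with specificity or severity not consistent with the risk information in the protocol/application", but Section 7.0 lists the expected effects without grades, and no text ties the 1-to-3 score to that flag.
- A metabolic panel is scheduled at screening and at Weeks 0, 2, 4 and 8, so the scheduled potassium values are recorded whatever grade is assigned.

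**The case against.** The strongest reply is that this is loose wording with little consequence. Grades 1 and 3 turn on what the event required, not on what was given, so a sensible grader would not call a study-ending potassium level mild. The serious flag, grades 4 and 5 and the laboratory values carry the important safety information. No planned analysis uses grades 1 to 3.

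Much of this stands. It limits the consequences, and it means that grades 1 and 3 do not follow mechanically from the response chosen. It does not repair the scale: need for treatment is still not intensity, grade 2 depends expressly on what treatment achieved, and the overlap and the gap follow from the words alone. A grader's good sense is not a rule that two graders will apply alike.

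A reader might infer three stronger things that the documents do not support:

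- **That the two drugs receive opposite potassium grades as written.** The documents attach no direction of potassium change to either drug. Sections 6.0 and 7.0 give one management rule for electrolyte imbalance in all arms, and grade 3 is admissible for all three potassium events above. The text permits a reversed ranking but does not determine one.
- **That severity cannot be compared between arms at all.** Grades 4 and 5, the serious flag and the scheduled metabolic panels remain comparable.
- **That expedited reporting is distorted.** A choice among grades 1, 2 and 3 cannot by itself trigger the report, because seriousness is also required and is judged separately.

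**Conclusion.** The point holds for grades 1 to 3. As printed they overlap, leave some treated but unresolved events without a grade, and can rank a trivial treated symptom above an intense untreated one. A single potassium event can have two or three admissible grades. Grades 1 to 3 in the logs and annual summary are therefore not a reliable measure of severity, within or between arms.

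The overlap and the gap need no assumption beyond the printed words. The potassium examples rest on the two open readings in step 4 and, for the second event, on the assumption that no treatment was given. The share of events affected is unknown. No planned efficacy result is shown to change. The correction is still worth making, because the scale applies to every adverse event and the bodies overseeing safety see its output.

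**What to change.** In Section 8.0 and on the adverse-event form, redefine grades 1 to 3 as mutually exclusive and exhaustive levels of intensity:

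- for symptoms, by effect on usual activities;
- for laboratory abnormalities, by bands of the measured value that the investigators prespecify.

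Record treatment given, action taken and outcome as separate fields, so that the information now mixed into the grade is kept. Leave grades 4 and 5, the definition of serious, and all management and stopping rules as they are.

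The cost is a change of wording and form, plus one re-grading pass from source for events already graded. Laboratory events can be re-graded from recorded values. Symptoms can be re-graded only as far as the interview notes describe intensity, and those that cannot should be marked as such. No new visit, test or procedure is needed.
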